# 7.3 Reporting

Any UPIRSO that occurs during the conduct of this study and that meets all three criteria listed in 9.4.3 must be reported to the UNC IRB using the IRB's web-based reporting system.

# 7.4 Data and Safety Monitoring Plan

The Principal Investigator will provide continuous monitoring of patient safety in this trial with periodic reporting to the Data and Safety Monitoring Committee (DSMC) as required.

Meetings/teleconferences will be held at a frequency dependent on study accrual, and in consultation with the study Biostatistician. At these meetings, the research team will discuss all issues relevant to study progress, including enrollment, safety, regulatory, data collection, etc. and the team will produce summaries or minutes of these meetings. These summaries will be available for inspection when requested by any of the regulatory bodies charged with the safety of human subjects and the integrity of data including, but not limited to, the oversight Office of Human Research Ethics (OHRE) Biomedical IRB, the Oncology Protocol Review Committee (PRC) or the North Carolina TraCS Institute Data and Safety Monitoring Board (DSMB).

## 8.0 STATISTICAL CONSIDERATIONS

## 8.1 Study Design

This project was originally designed as a randomized, prospective, phase 0 clinical trial in which half of the patients who undergo surgical staging for EC will be

randomized to a HIIT intervention group receiving 4 to 8 session of home-based HIIT (approximately 2-3 wks of HIIT), and the other half receiving standard of care treatment (i.e. no exercise intervention), prior to hysterectomy. The effect of HIIT on proliferation and apoptosis will be compared between pre-intervention endometrial biopsies and post-intervention hysterectomy/endometrial biopsy specimens. Expression of regulators of insulin/IGF-1/fatty acid/lipid synthesis pathways will be compared pre- and post-HIIT intervention in ECs.

Slow accrual due to COVID-19 pandemic prevent us from completing the study in time. As COVID-19 pandemic is still on-going, we decided to change the study design to a prospective single arm study with all new accruals assigned to the HIIT arm, till we have a total of 20 evaluable (i.e., with complete pre- and post-HIIT data) patients in the HIIT arm.

# 8.2 Sample Size and Accrual

The original sample size description: Based on data from our previous studies, we expect a difference of 13% (SD = 14%) for pre-post change in Ki-67 proliferation, and a difference of 1.7 (SD = 1.8) ml·kg·min for pre-post change in VO2peak, and attrition not greater than 10%. Under these assumptions, having 22 (20 evaluable) subjects per arm would detect the expected differences in both primary endpoints with at least 75% power and 2-sided  $\alpha$ =0.025 (Bonferroni adjustment).

The updated sample size description: Based on data from our previous studies,  we expect a difference of 10.3% (SD = 14%) for pre-post change in Ki-67 proliferation, and a difference of 1.8 (SD = 2.5) ml·kg·min for pre-post change in VO2peak in the HIIT arm, and attrition not greater than 10%. Historically, the pre-post change in Ki-67 and in VO2peak under usual care are 0. Under these assumptions, having 20 evaluable subjects in the HIIT arm would detect the expected differences in both primary endpoints with at least 80% power and 2-sided  $\alpha$ =0.025 (Bonferroni adjustment).

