# 2.2 Exploratory Objectives

# 3.0 STUDY ENDPOINTS

# 3.1 Primary Endpoints

3.1.1 Change in Ki-67 proliferation values within HIIT intervention group between initial biopsy and surgical biopsy

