# **Data Analysis Plans**

The original data analysis plan: Appropriate descriptive statistics for relevant variables (e.g., Ki-67 proliferation, VO2peak, p-mTOR expression, time to exhaustion, etc.) will be calculated by arm and by time (baseline and week 3). For pre-post changes of Ki-67 and VO2peak, the two primary endpoints (and similarly for other variables), differences between groups (HIIT vs. no-HIIT) in Ki-67 (or VO2peak) will be analyzed using analysis of covariance (ANCOVA) with baseline Ki-67 (or VO2peak) used as the covariate.

Our primary analysis will follow the intent-to-treat (ITT) principle, like for many randomized clinical trials. For the primary analysis, we will use a conservative (but valid) approach, and only include key covariates like baseline Ki67 level, stratification factors, in addition to HIIT (treatment assignment). In the exploratory

analysis, we will include adherence and other covariates in the model. Findings from exploratory analysis will be used for hypothesis generation.

The updated data analysis plan: Appropriate descriptive statistics for relevant variables (e.g., Ki-67 proliferation, VO2peak, p-mTOR expression, time to exhaustion, etc.) will be calculated by arm and by time (baseline and week 3).

Our primary analysis will be on pre-post changes in Ki-67 and VO2peak for patients in the HIIT arm and to test whether the differences were significantly different from 0 using Wilcoxon signed rank test.

For now, there are 10 patients randomized to the usual care arm have completed the study. To make good use of the data, we will conduct an exploratory analysis to compare the differences between groups (HIIT vs. no-HIIT) in Ki-67 (or VO2peak), which will be analyzed using analysis of covariance (ANCOVA) with baseline Ki-67 (or VO2peak) used as the covariate (we will also conduct similar exploratory analyses for other variables). We may also include adherence and other covariates in the model. Findings from exploratory analysis will be used for hypothesis generation.

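### With 20 evaluable patients and normally distributed changes, the planned Wilcoxon test has about 77% power for Ki-67 and 75% for VO2peak, not at least 80% for both

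*Combined protocol and SAP*

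**What the plan says.** The updated sample size description in section 8.2 gives the planning values. For Ki-67, "we expect a difference of 10.3% (SD = 14%) for pre-post change in Ki-67 proliferation"; for VO2peak, the expected change is 1.8 with SD 2.5 ml/kg/min. Changes "under usual care are 0", so the null value is zero. From these it concludes that "having 20 evaluable subjects in the HIIT arm would detect the expected differences in both primary endpoints with at least 80% power", with two-sided alpha 0.025 for each endpoint after a Bonferroni split.

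The updated analysis plan, under Data Analysis Plans, makes changes in both Ki-67 and VO2peak the primary analysis, to "test whether the differences were significantly different from 0 using Wilcoxon signed rank test". Section 8.1 defines evaluable patients as those with complete pre- and post-HIIT data, so the 10% attrition allowance is already outside the 20.

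Section 3.1 lists a single primary endpoint: "Change in Ki-67 proliferation values within HIIT intervention group between initial biopsy and surgical biopsy".

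Section 8.2 does not say which power formula or software was used, or what distribution the changes were assumed to follow.

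**The concern.** The standardised changes are a little above 0.7, the sample is 20, and the per-endpoint alpha is 0.025. At that size, formulas that treat the SD as known overstate power noticeably. The power statement is worded as a floor for both endpoints and is the only statistical reason given for stopping at 20 evaluable patients. It should therefore hold for the test that will be run.

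At stake is how a non-significant result is read. A reader would take the type II error to be at most 20% on each endpoint. If power for VO2peak is about 75%, that risk is about 25%.

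**Working it through.** **Inputs.** From section 8.2 (updated description): n = 20 evaluable; Ki-67 change 10.3, SD 14; VO2peak change 1.8, SD 2.5; null value 0; two-sided alpha 0.025. From Data Analysis Plans (updated): Wilcoxon signed rank test. The distribution of the changes is not given. Normality is assumed first, and a range follows.

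**Standardised changes.** Ki-67: 10.3/14 = 0.736. VO2peak: 1.8/2.5 = 0.720.

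**Reproducing the stated figure.** The large-sample formula with known SD is power = Φ(d√n − z), with z = 2.241 for two-sided 0.025.

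- Ki-67: 0.736 × √20 = 3.290; Φ(3.290 − 2.241) = Φ(1.049) = 85.3%.
- VO2peak: 0.720 × √20 = 3.220; Φ(3.220 − 2.241) = Φ(0.979) = 83.6%.

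Replacing n by 20 × 3/π, the large-sample efficiency of the Wilcoxon test under normality, gives Φ(3.215 − 2.241) = 83.5% and Φ(3.147 − 2.241) = 81.7%. Either version supports at least 80% for both, so the statement is consistent with a large-sample approximation and is not an arithmetic slip. The same kind of approximation reproduces the original two-arm claim of at least 75% (75.6% and 77.2%), which suggests, but does not prove, that it was the method used.

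**Paired t-test.** This needs no simulation. With 19 degrees of freedom, critical value 2.433 and noncentrality 3.290 or 3.220, power is 79.6% for Ki-67 and 77.7% for VO2peak. Estimating the SD from 20 patients is enough to bring both below 80%.

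**The named test.** The null distribution of the signed rank statistic is known exactly for n = 20. The test rejects when the smaller rank sum is 45 or less, which has two-sided size 0.02395; the next value would exceed 0.025. Power was simulated with 400,000 replicates per case (Monte Carlo standard error at most 0.08 percentage points), with every distribution scaled to the plan's mean and SD:

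| Distribution of changes | Ki-67 | VO2peak |
|---|---|---|
| Normal | 77.4% | 75.5% |
| Logistic | 80.9% | 79.1% |
| t, 5 df | 84.2% | 82.7% |
| Laplace | 84.4% | 83.1% |
| Uniform | 70.8% | 68.6% |

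Under normality the shortfall from 80% is 80 − 77.4 = 2.6 points and 80 − 75.5 = 4.5 points.

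**Scale of the gap.** With normal changes and n = 20, the exact test reaches 80% power at a change of 0.759 SD. That is 0.759 × 14 = 10.6 for Ki-67 (plan: 10.3) and 0.759 × 2.5 = 1.90 ml/kg/min for VO2peak (plan: 1.8). In patients, 22 evaluable give 81.6% and 79.5%, and 23 give 83.7% and 82.0%.

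**Ki-67 alone at two-sided 0.05.** The exact size is 0.04844. Power is 86.0% with normal changes and 80.9% to 90.8% over the other four distributions.

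**The case against.** The strongest reply is that a standard planning formula for the named test returns more than 80% on both endpoints, and that normality is not in the plan. A rank test does not require it, and with heavier tails (t with 5 df, Laplace) the claim holds for both endpoints. That is true, and it is why 77% and 75% can be stated only conditionally. It does not rescue the claim as written. Under normality the exact test misses, and so does the more efficient t-test. Logistic changes miss on VO2peak, and uniform changes miss by about 9 and 11 points. A floor that needs heavy tails has to say so.

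Section 8.2 also cites, among its sources, a paper on sample size for common nonparametric tests (reference 50). Noether's signed-rank formula with normal changes gives 68.3% and 66.9%. It is rough at effects this large, so no weight is placed on it here, but it does not support 80%.

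Two further points stand. The shortfall exists only while both endpoints are primary at 0.025; with Ki-67 alone at 0.05 the target is met, so the endpoint question should be settled along with this sentence. And the post-surgical VO2peak test is optional (sections 5.1 and 6.1). The 75% assumes 20 patients who all have it, which fits the definition of evaluable but may be optimistic in practice.

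It is also fair to say that this is a phase 0 study redesigned for slow accrual and that the gap is small. That limits the importance of the point, not its correctness.

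**Conclusion.** The concern holds. The plan's own n, alpha, effect sizes and named test give about 77% power for Ki-67 and 75% for VO2peak when changes are normally distributed. The only assumption added is the distribution, on which the plan is silent; over the five distributions examined, power runs from 68.6% to 84.4%. The unconditional claim of at least 80% for both endpoints is therefore unsupported. The shortfall is modest, does not affect the validity of the planned test, and disappears if Ki-67 is the single primary endpoint at two-sided 0.05.

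**What to change.** Keep the sample size and replace the power sentence in section 8.2. If both endpoints stay primary:

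*Assuming normally distributed changes, 20 evaluable patients give the Wilcoxon signed rank test about 77% power for Ki-67 and 75% for VO2peak, each at two-sided 0.025.*

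If Ki-67 is the single primary endpoint, as in section 3.1:

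*Assuming normally distributed changes, 20 evaluable patients give the Wilcoxon signed rank test about 86% power for Ki-67 at two-sided 0.05.*

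If the sponsor has grounds for another distribution, the sentence should name it and the method used. The cost is one sentence, with no change to the sample size, the test or the conduct of the study. At 0.025 the stated power falls by about 3 points for Ki-67 and 5 for VO2peak.

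### If Ki-67 and VO2peak both stay primary, Holm should replace plain Bonferroni at 0.025 each; but sections 2.1 and 3.1 name only Ki-67, and that conflict must be settled first

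*Combined protocol and SAP*

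**What the plan says.** **Sample size (8.2, updated description).** The single-arm study is sized on two primary endpoints. For Ki-67, "we expect a difference of 10.3% (SD = 14%) for pre-post change in Ki-67 proliferation". For VO2peak, the expected change is 1.8 with SD 2.5. Both changes "under usual care are 0". The conclusion is that "having 20 evaluable subjects in the HIIT arm would detect the expected differences in both primary endpoints with at least 80% power", at two-sided "0.025 (Bonferroni adjustment").

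**Analysis (8.2, Data Analysis Plans, updated).** The primary analysis covers the pre-post changes in both variables, "to test whether the differences were significantly different from 0 using Wilcoxon signed rank test". No step-down rule, hierarchy or other multiplicity procedure is named.

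**Objectives and endpoints (2.1, 3.1).** The only primary objective concerns the anti-proliferative effect, and the only primary endpoint is the Ki-67 change. VO2peak is not listed.

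**Availability of VO2peak (5.1 schema footnote 4; 6.1 footnote 3).** The post-surgical VO2peak test is optional. Section 8.1 counts patients who are "evaluable (i.e., with complete pre- and post-HIIT data) patients in the HIIT arm" and does not say whether VO2peak must be among those data.

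**The concern.** Two matters are linked. First, the number of primary tests is not settled: 8.2 splits alpha over two, while 3.1 has one. Second, if there are two, single-step Bonferroni is the less powerful of two equally simple rules with the same guarantee. Holm compares the smaller p-value with 0.025 and, if that is significant, the larger with 0.05. It controls the family-wise error at 5% under any dependence between the endpoints, and it rejects everything that Bonferroni rejects.

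In practice, Bonferroni calls a Ki-67 result with p between 0.025 and 0.05 negative even when VO2peak is clearly significant, and the reverse. With 20 patients and accrual slow enough to have forced the change to one arm, power that needs no extra patients is worth having.

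**Working it through.** **Inputs (8.2, updated).** n = 20 evaluable, so already after attrition. Standardized effects: Ki-67 10.3/14 = 0.736; VO2peak 1.8/2.5 = 0.720. Null value 0. Two-sided alpha 0.025 each. Test: Wilcoxon signed rank. The correlation between the two changes is not given; I assume a range of -0.3 to 0.8. Changes are assumed normal.

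**1. The plan's own figure.** The one-sample normal approximation is power = Φ(d√n − 2.241).
- Ki-67: Φ(3.290 − 2.241) = 85.3%.
- VO2peak: Φ(3.220 − 2.241) = 83.6%.

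Multiplying n by the Wilcoxon efficiency factor 3/π gives 83.5% and 81.7%. The stated figure of at least 80% is therefore reproduced, as power per endpoint.

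**2. The planned test at n = 20.** Power under other calculations:

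| Calculation | Ki-67, 0.025 | VO2peak, 0.025 | Ki-67, 0.05 | VO2peak, 0.05 |
|---|---|---|---|---|
| One-sample t (noncentral t) | 79.6% | 77.7% | 87.7% | 86.3% |
| Exact signed rank, simulated | 77.4% | 75.4% | 86.0% | 84.5% |
| Noether's formula | 68.3% | 66.9% | 77.6% | 76.4% |

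The exact signed-rank critical value at 0.025 is 45, with attained level 0.02395. Noether's formula is conservative here.

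**3. Holm with independent endpoints.** An endpoint is declared if its p is at most 0.025, or if its p lies between 0.025 and 0.05 and the other's is at most 0.025.
- Ki-67: 0.7744 + (0.8604 − 0.7744) × 0.7541 = 0.839.
- VO2peak: 0.7541 + (0.8449 − 0.7541) × 0.7744 = 0.824.
- Both, Bonferroni: 0.7744 × 0.7541 = 0.584.
- Both, Holm: 0.8604 × 0.8449 − 0.0860 × 0.0908 = 0.719.
- At least one: 94.5% under either rule.

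**4. Other correlations (simulated, Holm).**

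| Correlation | Ki-67 | VO2peak | Both |
|---|---|---|---|
| -0.3 | 84.5% | 83.0% | 71.1% |
| 0 | 83.9% | 82.5% | 71.9% |
| 0.5 | 82.7% | 81.4% | 74.6% |
| 0.8 | 81.7% | 80.6% | 77.2% |

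**5. Error rate.** With both nulls true, the simulated family-wise error is about 4.7% with independent endpoints, the same as Bonferroni. With one null true, the true-null endpoint is rejected in at most 4.3% of trials.

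**6. Where the gain shrinks (independent endpoints, Holm).**
- VO2peak effect halved: Ki-67 about 79%.
- VO2peak effect zero: Ki-67 0.7744 + 0.0860 × 0.0239 = 0.776, so practically no gain and no loss.
- VO2peak pairs on 15 patients: VO2peak power 68%.
- VO2peak pairs on 10 patients: VO2peak power 47% (33% under Bonferroni); Ki-67 about 80%, from 0.7744 + 0.0860 × 0.33 = 0.803.

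**7. Ki-67 as sole primary.** No split is needed, and signed-rank power at 0.05 is 86.0%, whatever happens to VO2peak.

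**The case against.** The strongest reply is that there may be no family of two. Sections 2.1 and 3.1 name only Ki-67, and the summary of the single-arm amendment records that a second primary endpoint was removed. On that reading Holm is moot, and writing it into 8.2 would entrench a leftover. This stands, and it is why reconciliation comes first. It does not rescue the present text, because with a single primary endpoint the 0.025 threshold is not needed either.

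A reader might infer that Bonferroni is what makes the plan miss its stated 80%. The documents do not support that. By the normal approximation both endpoints exceed 80% under Bonferroni. The shortfall appears only with t or exact signed-rank calculations, and it is a matter of power method. By Noether's formula (the paper is reference 50, cited in 8.2) even a full 0.05 does not reach 80%.

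A reader might also infer that Holm secures 80% for both endpoints whatever happens. It does not. The lift needs both assumed effects to be real and VO2peak pairs on all 20 patients, although the post-surgical test is optional. Requiring VO2peak for evaluable status is one reading of 8.1, but the documents do not settle it.

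Finally, Bonferroni gives something in return: simple simultaneous confidence intervals. Ordinary 97.5% intervals can still be reported beside Holm, but they may include 0 when Holm rejects at p between 0.025 and 0.05.

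**Conclusion.** The point holds in conditional form. The documents disagree on whether VO2peak is primary, and 8.2 must be reconciled with 2.1 and 3.1. If two primary endpoints remain, Holm is better than plain Bonferroni at no cost in error rate or patients: about 4 to 7 percentage points of power for Ki-67, 5 to 8 for VO2peak, and 13.5 for both together with independent endpoints (71.9 − 58.4). These figures rest on the plan's effects and SDs, normal changes, the exact signed-rank test, 20 complete pairs for each endpoint, and assumed correlations from -0.3 to 0.8. They concern power per endpoint; the chance of both being significant stays at 71-77% under Holm. The Bonferroni rule is valid and prespecified, so a reading that the plan contains an invalid test is not supported.

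**What to change.** 1. Reconcile 2.1 and 3.1 with 8.2 and the updated analysis plan on whether VO2peak is a primary endpoint.
2. If two primary endpoints are kept, replace the Bonferroni rule in 8.2, and state in the analysis plan: the smaller of the two Wilcoxon p-values is compared with 0.025; if it is significant, the other is compared with 0.05.
3. Restate the power for the Wilcoxon test under Holm, and note that the present 80% is met under Bonferroni only by a normal approximation. State whether evaluable requires a post-surgical VO2peak, and give VO2peak power for fewer pairs if it does not.
4. If Ki-67 is the sole primary endpoint, drop the split, test it at two-sided 0.05, and restate its power (about 86%).

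The cost is a few sentences, with no added patients, visits or assays. Because the study is under way, with 10 usual-care patients already complete, the amendment should be fixed before outcomes are examined and should say so. The remaining downside is the less simple match between intervals and tests.

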# **Data Analysis Plans**

The original data analysis plan: Appropriate descriptive statistics for relevant variables (e.g., Ki-67 proliferation, VO2peak, p-mTOR expression, time to exhaustion, etc.) will be calculated by arm and by time (baseline and week 3). For pre-post changes of Ki-67 and VO2peak, the two primary endpoints (and similarly for other variables), differences between groups (HIIT vs. no-HIIT) in Ki-67 (or VO2peak) will be analyzed using analysis of covariance (ANCOVA) with baseline Ki-67 (or VO2peak) used as the covariate.

Our primary analysis will follow the intent-to-treat (ITT) principle, like for many randomized clinical trials. For the primary analysis, we will use a conservative (but valid) approach, and only include key covariates like baseline Ki67 level, stratification factors, in addition to HIIT (treatment assignment). In the exploratory

analysis, we will include adherence and other covariates in the model. Findings from exploratory analysis will be used for hypothesis generation.

The updated data analysis plan: Appropriate descriptive statistics for relevant variables (e.g., Ki-67 proliferation, VO2peak, p-mTOR expression, time to exhaustion, etc.) will be calculated by arm and by time (baseline and week 3).

Our primary analysis will be on pre-post changes in Ki-67 and VO2peak for patients in the HIIT arm and to test whether the differences were significantly different from 0 using Wilcoxon signed rank test.

For now, there are 10 patients randomized to the usual care arm have completed the study. To make good use of the data, we will conduct an exploratory analysis to compare the differences between groups (HIIT vs. no-HIIT) in Ki-67 (or VO2peak), which will be analyzed using analysis of covariance (ANCOVA) with baseline Ki-67 (or VO2peak) used as the covariate (we will also conduct similar exploratory analyses for other variables). We may also include adherence and other covariates in the model. Findings from exploratory analysis will be used for hypothesis generation.

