## AMENDMENT RATIONALE AND SUMMARY:

This amendment will change the BMI inclusion criteria to help with accrual. We are decreasing the lower BMI limit of 30 to  $25 \text{kg/m}^2$ , to include both obese and overweight women as all would potentially benefit from HIIT. The upper limit will remain  $55 \text{kg/m}^2$ .

- 1. Updated Sections 1.1, 1.2, and 1.3 to reflect inclusion of obese/overweight women
- 2. Updated Section 2.2.2.2 in Exploratory Objectives to include obese/overweight analysis
- 3. Updated Sections 4.1 and 5.3 to reflect new BMI range of 25-55kg/m^2
- 4. Updated Sections 5.1, 5.3, and 5.3.6 to reflect inclusion of obese/overweight women.

LCCC 1839: Pre-operative Window Study of Interval Exercise Training as a Therapy for Endometrial Cancer

AMENDMENT INCORPORATES	(check	all that	apply):
Editorial, administrative changes			

Scientific changes

\_X\_ Study Design changes

Eligibility Changes

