## AMENDMENT RATIONALE AND SUMMARY:

This amendment changed the study design from a two-arm randomized study to a single-arm (HIIT arm only) study. This change is a result of a slower than expected accrual due to the COVID-19 pandemic. The pandemic halted all recruitment for 6 months; upon reopening new patient appointments for early stage cancers are down approximately 30%. Our team has already gained an incredible amount of insight and some good data that can be used to inform future studies to support endometrial cancer. Per the recommendation of our recent LCCC PRC review, we met with our program officer about the slower than expected accrual, and our program officer agreed with changing this study to a single arm intervention study. All new accruals will be assigned to the HIIT arm. We plan to have a total of 20 evaluable patients in the HIIT arm at the end of this study. Here, 'evaluable' means to have complete pre-HIIT and post-HIIT data.

- 1. Updated Sections 1.1 and 1.3 to show that this is no longer a randomized trial.
- 2. Removed study objectives in Section 2.1.2
- 3. Removed second primary endpoint in Section 3.1.2
- 4. Updated schema in Section 5.1 and removed mention of control arm
- 5. Removed all comparisons and explanations regarding the control arm in Section 5.2
- 6. Added mention of Complex Atypical Hyperplasia patients and removed control group comparisons in Section 5.3
- 7. Removed control group comparisons in Sections 5.3.5, 5.3.6 and 5.3.7
- Time and Events Table in Section 6.1 updated to show that VO2 is optional during postop
- 9. Study Design in Section 8.1 updated to show that this is now a one arm trial with only HIIT participants
- 10. Sample Size Description and Data Analysis were updated in Sections 8.2

LCCC 1839: Pre-operative Window Study of Interval Exercise Training as a Therapy for Endometrial Cancer

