## AMENDMENT RATIONALE AND SUMMARY:

This amendment expands eligibility criteria to reflect the patients seen in our clinic. Eligibility now includes those with a diagnosis of complex endometrial hyperplasia, which has similar biology as it is a precursor to endometrial cancer. The BMI and age requirements were also updated to reflect the patient population seen in clinic and boost accrual.

- 1. Eligibility criteria 4.1.1 updated to include complex endometrial hyperplasia
- 2. Eligibility criteria 4.1.4 was deleted due to redundancy
- 3. Age range expanded in 4.1.2 to include patients 30 -75 years of age instead of 40-75 years old.
- 4. The upper limit of BMI was changed in 4.1.3 to a maximum of 55.
- 5. Schema 5.1 updated to indicate VO2 peak at post-surgical testing is optional.

LCCC 1839: Pre-operative Window Study of Interval Exercise Training as a Therapy for Endometrial Cancer

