#### **5.3.1 Structured Interview:**

A structured one-on-one interview will occur with participants after completion of the HIIT program. The interview will be used to learn about barriers and concerns they experienced with regard to the current training protocol; preference of exercise mode and instruction; and opinions on what information participants would find helpful to improve the at-home training experience. While we do not intend to formally analyze the interview responses, we do anticipate that they will be useful for refining our intervention program for future trials.

- **5.3.2 Tolerability, Feasibility, Compliance, and Adherence:** Adherence and tolerability will be evaluated based on number of sessions attended/completed, modifications, such as change in mode, number of training days per week, and recovery days needed between sessions to complete training. The physical activity enjoyment scale will be given to assess participant enjoyment of exercise during the baseline and post-surgical testing visit.
- 5.3.3 To determine if HIIT decreases proliferation and induces apoptosis in the endometrial tumors, tissue microarrays (TMAs) will be constructed and immunohistochemical (IHC)analysis performed to assess Ki-67 staining (marker of proliferation) and caspase-3 expression (marker of apoptosis). The percentage of Ki-67 positive cells, termed the Ki-67 index, will be calculated pre- and post-treatment. Apoptosis will be evaluated by changes in activated caspase-3 expression. Individual slides will be digitized and analyzed using the Aperio ScanScope (Aperio Technologies, Vista, CA). This work will be performed with the expertise of the UNC-CH Translational Pathology Lab (TPL).
- **5.3.4** To test if HIIT alterations inhibits downstream targets of the insulin/IGF-1/AMPK/mTOR signaling pathway, IHC analyses of the ECs will be performed to determine expression of key targets of the insulin/IGF-1/mTOR pathway pre- and post-intervention, including p-IRS-1, p-IGF1R, p-AMPK, p-mTOR, p-Akt, p-S6, and p-4EBP-1.

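### The exploratory HIIT versus usual-care ANCOVA mixes randomised and later non-randomised HIIT patients, and it may adjust for adherence, which controls cannot have

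*Combined protocol and SAP*

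**What the plan says.** Section 8.1 explains that a two-arm randomised trial became a "prospective single arm study with all new accruals assigned to the HIIT arm", continuing until 20 HIIT patients are evaluable. The single-arm amendment summary says the same: "All new accruals will be assigned to the HIIT arm".

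The updated Data Analysis Plans in section 8.2 make the primary analysis a Wilcoxon signed rank test of change within HIIT. They then note that "there are 10 patients randomized to the usual care arm have completed the study" and plan an exploratory ANCOVA of HIIT against no HIIT, with baseline Ki-67 (or VO2peak) as the only named covariate. Two sentences follow: "We may also include adherence and other covariates in the model" and "Findings from exploratory analysis will be used for hypothesis generation".

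Section 5.3.2 defines the optional covariate: "Adherence and tolerability will be evaluated based on number of sessions attended/completed", together with changes of mode, training days and recovery days. Section 8.1 describes usual care as having no exercise intervention.

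On eligibility, the BMI amendment summary states "We are decreasing the lower BMI limit of 30 to" 25 kg/m² and leaves the upper limit at 55. The eligibility amendment summary had set that limit: "The upper limit of BMI was changed in 4.1.3 to a maximum of 55".

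**The concern.** This ANCOVA is the only model that uses the trial's own controls. Two features make its arm coefficient hard to interpret.

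**Who is in the HIIT group.** All 10 controls were randomised. The HIIT group combines patients randomised alongside them with patients enrolled later who have no concurrent controls. The plan has no randomised-only analysis, no enrolment-period term and no count of randomised HIIT patients. The arm coefficient can therefore absorb changes over calendar time, including those across the six-month recruitment halt.

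It may absorb BMI differences too. The amendment summaries appear to be stacked newest first: the BMI summary retains an upper limit set in the eligibility summary, and the single-arm summary lies between the two. If that order is right, women with BMI 25 to 29.9 can be found only in the HIIT group.

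**What adherence means for a control.** Adherence arises after assignment and is built on sessions that controls were never offered. If it is left missing, all 10 controls drop out and no comparison remains. If it is set to 0, it nearly duplicates the arm indicator.

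At stake is what later studies take from this comparison. A pooled result could be read as randomised evidence, and a raw adherence term could hide a real difference.

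**Working it through.** **Inputs.** From the documents: 20 HIIT and 10 usual-care patients (sections 8.1 and 8.2); Ki-67 change of 10.3 points with SD 14 (section 8.2, updated sample size); 4 to 8 sessions (section 5.3). Assumed, because the documents do not give them: the number of HIIT patients randomised, any cohort difference, the spread of sessions, the coding of adherence, SD 14 in both groups, and two-sided 0.05 for this exploratory model.

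**The plan's own figure.** Section 8.2 gives no power for this ANCOVA. Its figure of at least 80% belongs to the one-sample primary tests at two-sided 0.025. A normal approximation reproduces it: 85.3% for Ki-67 and 83.6% for VO2peak. Nothing below depends on it.

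**Pooling.** Let D be the difference in mean Ki-67 change between later and randomised HIIT patients for reasons other than HIIT. Then bias = (20 − randomised HIIT)/20 × D. The false-positive rate comes from simulated two-sample t tests with no HIIT effect (20,000 per case), nominal 5%.

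| HIIT randomised | D = 2: bias, false positives | D = 5 | D = 10 |
|---|---|---|---|
| 15 of 20 | 0.5, 5.2% | 1.25, 5.4% | 2.5, 6.5% |
| 10 of 20 | 1.0, 5.4% | 2.5, 7.0% | 5.0, 12.6% |
| 5 of 20 | 1.5, 6.0% | 3.75, 10.0% | 7.5, 24.8% |

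The bias runs from 0.5/10.3 = 5% to 7.5/10.3 = 73% of the planned effect.

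**Adherence as raw sessions, controls at 0.** The variance inflation for the arm coefficient is VIF = 1/(1 − r²) = (between-arm SS + within-HIIT SS)/(within-HIIT SS), where SS is the sum of squares of sessions. The between-arm SS is (20 × 10/30) × (mean HIIT sessions)².

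- Four patients at each of 4, 5, 6, 7 and 8: mean 6, between 240, within 40. VIF = 280/40 = 7.0, r = 0.926, SE × 2.65.
- 2, 5, 6, 5 and 2 patients at 4 to 8: between 240, within 26. VIF = 266/26 = 10.2, r = 0.950, SE × 3.2.
- A wider assumed spread over 0 to 8 (mean 4.65): between 144.15, within 114.55. VIF = 258.7/114.55 = 2.26, r = 0.746, SE × 1.5.
- Any spread centred within HIIT: r = 0, VIF = 1.0.

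Without adherence, the SE of the arm effect is 14 × √(1/20 + 1/10) = 5.42 points. Noncentral-t power for 10.3 points, charging for the estimated baseline term but giving no credit for any variance it explains:

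| Model | Power |
|---|---|
| Baseline only | 43.6% |
| + raw sessions, even 4–8 | 10.4% |
| + raw sessions, clustered 4–8 | 8.7% |
| + raw sessions, 0–8 | 22.3% |
| + sessions centred within HIIT | 43.5% |

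In 8,000 simulated ANCOVAs with the even spread and an effect proportional to sessions, the mean arm coefficient was −10.4 without adherence, 0.03 with raw sessions and −10.4 with centred sessions.

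**Precision of a randomised-only comparison.** Two-sample t, no covariate, d = 10.3/14 = 0.7357; half-width = t(0.975) × 14 × √(1/n + 1/10).

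| HIIT v usual care | Power | 95% CI half-width |
|---|---|---|
| 5 v 10 | 24% | 16.6 |
| 10 v 10 | 34% | 13.2 |
| 15 v 10 | 41% | 11.8 |
| 20 v 10 (pooled) | 45% | 11.1 |

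A normal approximation gives slightly higher powers (27%, 38%, 44% and 48%), which does not change the picture.

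**The case against.** The plan labels this analysis exploratory and hypothesis-generating, and the remaining primary objective and endpoint are within HIIT. The documents say openly that later patients were assigned to HIIT, and they do not claim that randomisation protects the contrast. Adherence is optional, and the collapse in power needs one particular coding; centred sessions do no harm. The largest pooling figures need both a small randomised share and a cohort difference close to the whole planned effect; in the middle case the false-positive rate is 7%. The permitted other covariates could include BMI or enrolment period. The randomised-only interval is wider than plus or minus 10.3 points in every case considered.

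Most of this stands as a limit on weight. It does not remove the point. An exploratory label does not tell the reader which HIIT patients had concurrent controls, and it gives no meaning to a covariate undefined in one arm. An unnamed covariate is not a plan. The pooled interval, at 11.1 points, also exceeds the planned effect, so low precision is no reason to prefer it over the randomised comparison. The controls' own change will still appear in the by-arm descriptive statistics, so the assumption of zero change under usual care can be examined without this model.

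**Conclusion.** The concern holds. As written, the between-group contrast is not protected by randomisation, and the optional adherence term has no defined value for controls.

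The pooling bias ranges from 0.5 to 7.5 Ki-67 points over the assumed cases, and could be near zero if later patients resemble the randomised ones. With raw coding, the adherence term cuts power from about 44% to between 9% and 22%, and drives the arm coefficient to about 0 if the effect is proportional to sessions. The BMI imbalance rests on an inferred amendment order, but the pooling point does not need it. The primary analysis is untouched, so this is a change that should be made rather than one on which the trial's main result depends.

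**What to change.** In the updated Data Analysis Plans:

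1. State that adherence is not entered in the HIIT versus usual-care model. Relate sessions completed to change in Ki-67 or VO2peak within the HIIT arm only.
2. Report the baseline-adjusted ANCOVA first in concurrently randomised patients, meaning HIIT and usual-care patients enrolled before the single-arm switch. Read it as an estimate with its interval.
3. Then report the model in all patients with baseline BMI added, labelled as a non-randomised comparison and kept as a sensitivity analysis. If there are no controls below BMI 30, say that the adjustment there is extrapolation.
4. State how many HIIT patients were randomised.

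The cost is SAP wording and one extra model on data already collected. The randomised-only comparison is less precise: half-width 11.8 to 16.6 points for an assumed 15 down to 5 randomised HIIT patients, against 11.1 pooled. Nothing is discarded, because the pooled analysis stays.
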